9.2 Data Analysis Plans

ROC analysis will be performed as the primary analysis for the first aim. To compare the results from the two imaging modalities, we will adopt the mixed effect ANOVA based on the Dorfman-Berbaum-Metz method. The outcome variable is the Tukey's jackknife pseudovalues of the AUCs from each reader and each patient under either modality, and separately for each anatomic region. The fixed effect in the independent list will correspond to the difference between the two modalities and the random effects will be used to account for within-patient and within-reader's correlations.

Possible interactions between the modalities and the readers and the patients will also be included and tested for statistical significance. To test the main hypothesis, F-test statistic from the model parameter estimates will be used to compare the mean AUCs between the b-mode ultrasound images and the CESR ultrasound images only.

9.3 Sample Size Considerations in ROC Analysis

For each lesion type, we assume 8 malignant and 7 benign and the AUC for conventional imaging to be 0.7 based on our previous breast studies. We will recruit patients with high TIRADS risk scores (4c, moderately

suspicious and 5, high risk), that have an anticipated risk range of a 50% to in excess of 85%, which will provide an estimated relative risk of 75% to be congruent with the breast population. The power to detect 0.2 AUC difference is about 30%. However, our primary goal is to evaluate the technical ability of the CESR approach to examine lesions in each of these superficial anatomic regions. We will also be evaluating the number of vessels visualized, the effects of respiratory motion and radiologist confidence in interpreting the CESR microvascular images. These studies will guide further development of the imaging approach for a prospective trial.

9.4 Secondary Analyses

Radiologist Preference

The secondary analysis will be to evaluate reader preference for specific lesion characteristics. To assess the reader preference for modality for each characteristic including shape, margins and vascularity, we will fit a random effect model with only intercept and random terms for patients and readers while the outcomes are the confidence scores (-3 to +3). By testing the intercept significantly larger than zero, we will conclude that the new modality provides more confidence for readers than the conventional one.

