2.2 Secondary Objectives

- 2.2.1** To compare (using a reader study) the sensitivity and specificity of contrast enhanced super-resolution imaging to the sensitivity and specificity of conventional b-mode ultrasound in evaluation of known breast lesions for predicting malignancy.
- 2.2.2** To compare (using a reader study) the sensitivity and specificity of contrast enhanced super-resolution imaging to the sensitivity and specificity of conventional b-mode ultrasound in evaluation of known thyroid lesions for predicting malignancy.
- 2.2.3** To compare the area under the curve (AUC) of contrast enhanced super-resolution imaging to the AUC of the b-mode ultrasound.
- 2.2.4** To compare radiologist preference of contrast enhanced super-resolution imaging to conventional b-mode ultrasound for each lesion characteristic (shape, margins, and vascularity).

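### The preference model in section 9.4 has no organ term and its conclusion is not limited by organ, so a preference in breast or thyroid alone can carry a general claim for CESR

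*Combined protocol and SAP*

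**What the plan says.** Section 9.4 states its purpose as follows: "To assess the reader preference for modality for each characteristic including shape, margins and vascularity". For each characteristic, "we will fit a random effect model with only intercept and random terms for patients and readers"; the outcome is the comparative confidence score from Appendix A, on a scale from -3 to +3. The decision rule is: "By testing the intercept significantly larger than zero, we will conclude that the new modality provides more confidence for readers than the conventional one". Organ appears neither in the model nor in the conclusion. No significance level is given.

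Objective 2.2.4 is likewise set per characteristic, without an organ: "To compare radiologist preference of contrast enhanced super-resolution imaging to conventional b-mode ultrasound for each lesion characteristic". The Appendix A form has fields for specimen, reader and date, but none for organ.

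Elsewhere the plan does separate the organs. Objectives 2.1.1 and 2.1.2, and again 2.2.1 and 2.2.2, treat breast and thyroid separately. Sections 9.2 and 4.2.5 analyse the AUC pseudovalues "and separately for each anatomic region". Section 9.3 gives the study's main goal as to "evaluate the technical ability of the CESR approach to examine lesions in each of these superficial anatomic regions", lists radiologist confidence among the things to be evaluated, and says the results will guide further development. Section 4.2.5 recruits five readers for each reader study and does not say whether the two organs share a panel.

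**The concern.** With an intercept as the only fixed term and 15 lesions per organ, the quantity tested is the plain average of the breast mean and the thyroid mean. Any gap between the organs is absorbed into the patient variance, and partly into the reader variance if the panels differ. A positive intercept then supports a statement about the modality in general.

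A strong preference in one organ can produce that statement when readers see no benefit in the other, or even favour b-mode there. The result also cannot say where CESR helps, which is what a pilot in two organs is meant to inform. An analyst following the text to the letter would split AUC by region and pool preference.

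**Working it through.** **Plan's own figure.** There is none for this analysis. The only power figure (about 30%, section 9.3) concerns AUC and is not an input here.

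**Inputs from the documents.** 15 breast and 15 thyroid patients (section 1.1); five readers (section 4.2.5); scores from -3 to +3; intercept-only model with random patients and readers (section 9.4).

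**Assumed, because the documents give no values.** Patient SD 0.7-1.0, reader SD 0.3-0.5, residual SD 0.8-1.0; organ means; one-sided level 2.5% or 5%; the same five readers for both organs unless stated.

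**Step 1: what the intercept estimates.** Score = mean + patient + reader + residual. With 15 lesions each, the pooled intercept is (breast mean + thyroid mean)/2. For +1 and 0 this is 0.5.

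**Step 2: where the gap goes.** With organ gap d, the apparent patient variance rises by (d²/4)(30/29). The variance of the intercept as the model sees it is

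[patient variance + (d²/4)(30/29)]/30 + reader variance/5 + residual variance/150.

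Take SDs 0.8, 0.3 and 0.8, and d = 1:

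- Added patient variance: 0.25 × 30/29 = 0.259.
- Pooled: (0.64 + 0.259)/30 + 0.09/5 + 0.64/150 = 0.0300 + 0.0180 + 0.0043 = 0.0522. SE 0.229, and 0.5/0.229 = 2.19.
- Breast alone: 0.64/15 + 0.09/5 + 0.64/75 = 0.0427 + 0.0180 + 0.0085 = 0.0692. SE 0.263, and 1/0.263 = 3.80.
- Thyroid alone: expected ratio 0.

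The pooled ratio lies just above 1.96, so a positive general conclusion in roughly half of trials is to be expected although thyroid shows nothing. Simulation at this setting gives 53.6% pooled, 92.7% breast alone and 2.8% thyroid alone.

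**Step 3: simulation.** Scores rounded and clipped to -3..+3, Satterthwaite t-test, one-sided 2.5%, 2,000 runs per scenario, (patient, reader, residual) SDs of (0.8, 0.3, 0.8), (0.8, 0.5, 0.8) and (1.0, 0.5, 1.0). Probability of a positive conclusion:

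| Breast / thyroid mean | Pooled | Thyroid alone | Breast alone |
|---|---|---|---|
| 0 / 0 | 2.0-2.5% | about 2% | about 2% |
| +1 / 0 | 31-54% | 2-3% | 71-93% |
| +1.5 / 0 | 55-84% | 2-3% | 97-100% |
| +1.5 / -0.5 | 24-37% | 0-0.1% | 96-100% |
| +2 / -0.5 | 46-67% | 0-0.1% | about 100% |
| +2 / -1 | 13-16% | 0% | about 100% |

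At one-sided 5%, with patient SD 0.7-1.0, reader SD 0.3-0.5 and residual SD 1.0, +1/0 gives 45-69% pooled, about 5% thyroid alone and 83-97% breast alone; +1.5/-0.5 gives 36-54% pooled. Repeat runs moved the ends of the +1/0 ranges by about one point, giving 31-55% and 44-70%. These ranges cover the settings run and are not bounds: the least variable corner of the assumptions goes a few points higher.

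With no preference in either organ, every test rejects at or near its nominal level. The test is therefore calibrated, and the other rows reflect averaging.

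**Step 4: separate reader panels.** With five different readers per organ and SDs 0.8, 0.3, 0.8 (400 runs), +1.5/0 gives 75-86% pooled and +2/-0.5 gives 22-38%, depending on whether a t value with 9 df or a normal critical value is used.

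**The case against.** **Pooling is not stated.** A reader might infer that the plan definitely combines the organs. It does not say so. Section 4.2.5 speaks of studies in the plural, two organs, and readers recruited for each reader study. If that means one study per organ with the preference model fitted inside each, the problem disappears. Nor is the silence of objective 2.2.4 strong evidence, because objective 2.2.3 on AUC names no organ either and is still analysed by region. This stands as a limit on the claim. But the phrase in 4.2.5 concerns recruitment, and the same section still spells out the split for AUC. Nothing applies it to preference.

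**No organ difference is predicted.** A reader might also infer that the plan expects different preferences in breast and thyroid, since section 9.3 mentions respiratory motion. That section only lists motion as something to evaluate. It does not say that motion differs by organ or affects preference. The gaps in the table are illustrations.

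**The pooled test is not wrong.** The percentages should not be read as false positive rates. With means of +1 and 0 the average preference is +0.5, and a positive test is correct for that average. The error arises when the result is taken to hold in each organ.

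**Pooling has merits.** If both organs benefit alike, 30 lesions are better than 15: at the step 2 setting with d = 0 the variance is 0.64/30 + 0.09/5 + 0.64/150 = 0.0436, SE 0.209, against 0.263 for one organ. Conclusions by organ also turn three tests into six. Both points stand, and they are reasons to keep the averaged estimate alongside the organ-specific ones.

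**Little depends on it.** No primary endpoint or safety matter is affected, and organ is known for every lesion, so by-organ summaries could be produced later. They would then be post hoc.

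**Conclusion.** The point holds in a limited form. As written, section 9.4 has no organ term, does not carry over the split by region used for AUC, and allows a conclusion about CESR in general. On the literal reading, a preference in one organ can carry that conclusion: in about 31-55% of trials at one-sided 2.5%, or 44-70% at one-sided 5%, for true means of +1 and 0 with shared readers. The probability is lower when the other organ favours b-mode (13-16% at +2/-1, one-sided 2.5%).

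These figures rest on assumed SDs, means, test level and reader panels, and show a mechanism, not a forecast. The documents do not establish that pooling is intended, that preference differs by organ, or that the test is invalid. Severity is low to moderate: it affects the interpretation of a secondary analysis in a pilot.

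**What to change.** In section 9.4:

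- Add organ (breast or thyroid) as a fixed effect in each characteristic's model, or fit the model by organ. If the panels differ, nest readers within organ.
- Report each organ's mean preference with its confidence interval, and the organ-averaged mean from the same model.
- State the conclusion only for the organ, or for the average, in which it is shown.
- Label the by-organ results as secondary and exploratory.

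If one reader study per organ was always intended, the same amendment should say so.

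The cost is a sentence or two and one model term, using data already to be collected. Section 4.2.5 places the reader study after accrual, so the change can be specified before any reading. The downside is that each organ's estimate rests on 15 lesions and there are more comparisons. The averaged estimate is not sacrificed: in the step 2 example, removing the organ gap from the patient variance takes its SE from 0.229 to about 0.209, at the price of one patient-level degree of freedom.

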10.0 STUDY MANAGEMENT

10.1 Institutional Review Board (IRB) Approval and Consent

It is expected that the IRB will have the proper representation and function in accordance with federally mandated regulations. The IRB should approve the consent form and protocol.

In obtaining and documenting informed consent, the investigator should comply with the applicable regulatory requirement(s) and should adhere to Good Clinical Practice (GCP) and to ethical principles that have their origin in the Declaration of Helsinki.

Before recruitment and enrollment onto this study, the patient will be given a full explanation of the study and will be given the opportunity to review the consent form. Each consent form must include all the relevant elements currently required by the FDA Regulations and local or state regulations. Once this essential information has been provided to the patient and the investigator is assured that the patient understands the implications of participating in the study, the patient will be asked to give consent to participate in the study by signing an IRB-approved consent form.

Prior to a patient's participation in the trial, the written informed consent form should be signed and personally dated by the patient and by the person who conducted the informed consent discussion.

10.2 Registration Procedures

Study participants will be registered into OnCore®, a web based clinical research platform by one of the Study Coordinators.

10.3 Data Management and Monitoring/Auditing

The images of all eligible enrolled subjects that are obtained and contribute to the ultimate diagnosis leading to biopsy will be de-identified for inclusion in the reader study. Copies of the clinical report forms as well as the de-identified images described in the preceding will be submitted for each case to the Study Coordinators for maintaining the study record and entering the data into a spreadsheet in preparation for the reader study.

As an investigator-initiated study, this trial may also be audited by the Lineberger Cancer Center audit committee as appropriate.

10.4 Adherence to the Protocol

Except for an emergency situation in which proper care for the protection, safety, and well-being of the study patient requires alternative treatment, the study shall be conducted exactly as described in the approved protocol.

10.4.1 Emergency Modifications

UNC investigators may implement a deviation from, or a change of, the protocol to eliminate an immediate hazard(s) to trial subjects without prior UNC's IRB/IEC approval/favorable opinion.

For any such emergency modification implemented, an IRB modification form must be completed by UNC Research Personnel within five (5) business days of making the change.

10.4.2 Single Subject Exceptions

10.4.3 Eligibility single subject exceptions are not permitted for Lineberger Comprehensive Cancer Center Investigator Initiated Trials under any circumstances. Other types of single subject exceptions may be allowed if proper regulatory review has been completed in accordance with Lineberger Comprehensive Cancer Center's Single Subject Exceptions Policy. Other Protocol Deviations/Violations

According to UNC's IRB, a protocol deviation is any unplanned variance from an IRB approved protocol that:

- Is generally noted or recognized after it occurs
- Has no substantive effect on the risks to research participants

- Has no substantive effect on the scientific integrity of the research plan or the value of the data collected
- Did not result from willful or knowing misconduct on the part of the investigator(s).

An unplanned protocol variance is considered a violation if the variance meets any of the following criteria:

- Has harmed or increased the risk of harm to one or more research participants.
- Has damaged the scientific integrity of the data collected for the study.
- Results from willful or knowing misconduct on the part of the investigator(s).
- Demonstrates serious or continuing noncompliance with federal regulations, State laws, or University policies.

If a deviation or violation occurs, please follow the guidelines below:

Protocol Deviations: UNC personnel will record the deviation in OnCore®, and report to any sponsor or data and safety monitoring committee in accordance with their policies. Deviations should be summarized and reported to the IRB at the time of continuing review.

Protocol Violations: Violations should be reported by UNC personnel within one (1) week of the investigator becoming aware of the event using the same IRB online mechanism used to report Unanticipated Problems.

Unanticipated Problems:

Any events that meet the criteria for “Unanticipated Problems” as defined by UNC’s IRB must be reported by the study team using the IRB’s web-based reporting system.

10.5 Amendments to the Protocol

Should amendments to the protocol be required, the amendments will be originated and documented by the Principal Investigator at UNC. It should also be noted that when an amendment to the protocol substantially alters the study design or the potential risk to the patient, a revised consent form might be required.

The written amendment, and if required the amended consent form, must be sent to UNC’s IRB for approval prior to implementation.

10.6 Record Retention

Study documentation includes all eCRFs, data correction forms or queries, source documents, Sponsor-Investigator correspondence, monitoring

logs/letters, and regulatory documents (e.g., protocol and amendments, IRB correspondence and approval, signed patient consent forms).

Source documents include all recordings of observations or notations of clinical activities and all reports and records necessary for the evaluation and reconstruction of the clinical research study.

Government agency regulations and directives require that all study documentation pertaining to the conduct of a clinical trial must be retained by the study investigator. In the case of a study with a drug seeking regulatory approval and marketing, these documents shall be retained for at least two years after the last approval of marketing application in an International Conference on Harmonization (ICH) region. In all other cases, study documents should be kept on file until three years after the completion and final study report of this investigational study.

10.7 Obligations of Investigators

The Principal Investigator is responsible for the conduct of the clinical trial at the site in accordance with Title 21 of the Code of Federal Regulations and/or the Declaration of Helsinki. The Principal Investigator is responsible for personally overseeing the treatment of all study participants. The Principal Investigator must assure that all study site personnel, including sub-investigators and other study staff members, adhere to the study protocol and all FDA/GCP/NCI regulations and guidelines regarding clinical trials both during and after study completion.

12.0 APPENDICES

12.1 Appendix A: Reader Study Data Collection Form

Specimen: _____

Reader: _____

Date: _____

Overall Assessment:

Primary

Overall specimen malignancy score (-2 to +2): _____
Malignancy confidence (0-100) _____ %

Secondary

Overall specimen malignancy score (-2 to +2): _____
Malignancy confidence (0-100) _____ %

1. Primary versus Secondary Shape/Morphology

+3	I am significantly more confident in the Primary representation of the lesion shape/morphology I described as compared to Secondary representation of the same lesion
+2	I am more confident in the Primary representation of the lesion shape/morphology I described as compared to Secondary representation of the same lesion
+1	I am slightly more confident in the Primary representation of the lesion shape/morphology I described as compared to the Secondary representation of the same lesion.
0	I have the same confidence in the Primary representation of the lesion shape/morphology I described as I do in the Secondary representation of the same lesion
-1	I am slightly less confident in the Primary representation of the lesion shape/morphology I described as compared to the Secondary representation of the same lesion.
-2	I am less confident in the Primary representation of the lesion shape/morphology I described as compared to the Secondary representation of the same lesion.
-3	I am significantly less confident in the Primary representation of the lesion shape/morphology I described as compared to the Secondary representation of the same lesion.

2. Primary versus Secondary: Vascularity

+3	I am significantly more confident in the Primary representation of the lesion vascularity I described as compared to the Secondary representation of the same lesion.
+2	I am more confident in the Primary representation of the lesion vascularity I described as compared to Secondary representation of the same lesion
+1	I am slightly more confident in the Primary representation of the lesion vascularity I described as compared to the Secondary representation of the same lesion.
0	I have the same confidence in the Primary representation of the lesion vascularity I described as I do in the Secondary representation of the same lesion.
-1	I am slightly less confident in the Primary representation of the lesion vascularity I described as compared to the Secondary representation of the same lesion.
-2	I am less confident in the Primary representation of the lesion vascularity I described as compared to the Secondary representation of the same lesion.
-3	I am significantly less confident in the Primary representation of the lesion vascularity I described as compared to the Secondary representation of the same lesion.

3. Primary versus Secondary Margins /Distribution

+3	I am significantly more confident in the Primary representation of the lesion margins/distribution I described as compared to Secondary representation of the same lesion
+2	I am more confident in the Primary representation of the lesion margins/distribution I described as compared to Secondary representation of the same lesion
+1	I am slightly more confident in the Primary representation of the lesion margins/distribution I described as compared to the Secondary representation of the same lesion.
0	I have the same confidence in the Primary representation of the lesion margins/distribution I described as I do in the Secondary representation of the same lesion
-1	I am slightly less confident in the Primary representation of the lesion Secondary representation of the same lesion.
-2	I am less confident in the Primary representation of the lesion margins/distribution I described as compared to the Secondary representation of the same lesion.
-3	I am significantly less confident in the Primary representation of the lesion margins/distribution I described as compared to the Secondary representation of the same lesion.

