4.2.2.2 Imaging Procedures

CESR imaging involves a research ultrasound scanner as well as conventional b-mode ultrasound to guide the location of the imaging. The conventional ultrasound will be conducted just prior to CESR imaging for localization. Imaging will be performed within the package insert guidelines for ultrasound system mechanical index (a measurement of output power) when imaging perflutren contrast agent (less than 0.8).

CESR imaging will be performed by trained medical personnel using mild compression to eliminate motion. Total imaging time is estimated to be less than 15 minutes. All image data will be de-identified and transferred for off-line analysis based on a study ID. The research images will NOT be interpreted or analyzed for clinical decisions related to the patient. The field of view of the research images will be limited to clinically identified

lesions. Incidental findings are not anticipated due to the sensitivity limitations of this imaging modality. Information regarding additional lesions or other incidental findings discovered during research imaging procedures will not be recorded or communicated to the patient or their provider because this imaging modality is not standard of care.

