4.2.5 Reader Study

[figure not shown]
A reader study will be performed after the completion of patient accrual to study lesion characteristics under CESR as compared to conventional b-mode ultrasound. In these pilot observational studies, the primary aim will be to evaluate the imaging approach for application in these two organs. We will also estimate the receiver operating characteristic (ROC) curve for the CESR system. For scientific rigor, a total of five readers who are not investigators on this study (radiologists trained in breast imaging or ultrasound imaging) will be recruited to participate for each reader study. The readers will be asked to assign a probability score (1 to 5) and confidence for each lesion for each modality (0 to 100%). ROC analysis will be performed as the primary analysis for the first aim. To compare the results from the two imaging modalities, we will adopt the mixed effect ANOVA based on the Dorfman-Berbaum-Metz method. The outcome variable is the Tukey's jackknife pseudovalues of the AUCs from each reader and each patient under either modality, and separately for each anatomic region. The fixed effect in the independent list will correspond to the difference between the two modalities, and the random effects will be used to account for within-patient and within-reader's correlations. Possible interactions between the modalities and the readers and the patients will also be included and tested for statistical significance. To test the main hypothesis, F-test statistic from the model parameter estimates will be used to compare the mean AUCs between the b-mode ultrasound images and the CESR ultrasound images only.

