9.1 Study Design/Study Endpoints

This is a prospective study to assess the diagnostic performance of the newly developed device. The **primary outcome of interest is the sensitivity and specificity of the super-resolution imaging device in the analysis of known breast and thyroid lesions as compared to pathological results of these lesions**. The sensitivity and specificity can be estimated non-parametrically as the proportion of the lesions which are distinguished as malignant versus non-malignant compared to the reference. This estimate will be calculated for each reader then averaged over all the readers. The standard error of the average sensitivity and specificity estimate will be calculated using the bootstrap method, where each patient is treated as independent unit with 5 ratings. The confidence interval of the final estimate will be provided using the normality assumption.

Furthermore, we will estimate the sensitivity and specificity of the b-mode ultrasound in this study and compare it with the sensitivity and specificity estimate of the CESR imaging using the bootstrap approach and the confidence interval of their differences will be provided using the normality assumption.

Malignancy scores of +1 and +2 will be considered malignant. Scores of -2, -1, and 0 will be considered not malignant. The confidence of malignancy will be used independently

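### Appendix A takes both malignancy scores for a lesion on one form, and no section sets reading order, masking between modalities or score lock, so the CESR versus b-mode comparisons, and in some orders CESR accuracy itself, are open to carry-over

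*Combined protocol and SAP*

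**What the plan says.** Section 4.2.5 has the reader study run after accrual, with "a total of five readers who are not investigators on this study" for each organ. Each reader gives a score and a confidence for each lesion under each modality.

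Appendix A (section 12.1) is the collection form. Under a single specimen, reader and date header it repeats the line beginning "Overall specimen malignancy score (-2 to +2" twice, once for Primary and once for Secondary, each with a confidence percentage. Three comparative items on shape, vascularity and margins follow, for example "I am significantly more confident in the Primary representation of the lesion shape/morphology I described as compared to Secondary representation of the same lesion" and, for margins, "I am significantly more confident in the Primary representation of the lesion margins/distribution I described as compared to Secondary representation of the same lesion". The form does not say which modality is Primary and has no field for reading order.

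The scores feed three analyses:
- Section 9.1 estimates CESR sensitivity and specificity (the primary outcome) per reader and averages over readers. It takes standard errors from a bootstrap "where each patient is treated as independent unit with 5 ratings".
- Section 9.1 also estimates b-mode accuracy, to "compare it with the sensitivity and specificity estimate of the CESR imaging using the bootstrap approach" (objectives 2.2.1 and 2.2.2).
- Objective 2.2.3 is "To compare the area under the curve (AUC) of contrast enhanced super-resolution imaging to the AUC of the b-mode ultrasound". Sections 4.2.5 and 9.2 test this with a Dorfman-Berbaum-Metz (DBM) F-test and call it the test of the main hypothesis.

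**The concern.** Objectives 2.2.1 to 2.2.3 are paired comparisons within reader and lesion. They compare the modalities as stand-alone tests only if each score reflects its own images. When both scores sit on one sheet, followed by items that require both image sets, nothing stops a reader from giving the second score with the first in mind, or both with all images open.

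The consequence depends on the order:
- **CESR first:** the b-mode score can borrow from CESR. The comparison is then biased against CESR, while CESR accuracy itself is untouched.
- **B-mode first, or both in view:** the primary CESR sensitivity and specificity describe CESR read with b-mode, and part of any gain may not belong to CESR.

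Because the order is not recorded, the direction of any bias could not be worked out afterwards.

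**Working it through.** **1. Do other sections close the gap?**
- Section 4.2.5: non-investigator readers. This concerns independence, not masking to the other modality.
- Section 10.3: images are de-identified. This hides the patient, not the other modality.
- Section 4.2.3: CESR is not interpreted before biopsy. This protects the clinical decision, not the reader study.
- Section 4.2.2.2: "The conventional ultrasound will be conducted just prior to CESR imaging for localization". This is acquisition order, not reading order.
- Section 9.4: a positive preference score favours the new modality, which implies that Primary means CESR. Filled in from the top, the form would then take CESR first, but nothing requires that.
- Section 9.2: the model has a modality effect, reader and patient random effects and interactions, but no order term. These terms and the patient-level bootstrap deal with correlation. A systematic shift in the second score stays inside the modality effect.

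**2. The plan's own figure.** Section 9.3 assumes 8 malignant and 7 benign lesions per organ and a conventional AUC of 0.7, and gives about 30% power for a 0.2 difference. The Hanley-McNeil variance is [A(1−A) + 7(Q₁−A²) + 6(Q₂−A²)]/56, with Q₁ = A/(2−A) and Q₂ = 2A²/(1+A). It is 0.0191 at A = 0.7 and 0.0072 at A = 0.9. With an assumed between-modality correlation of 0.3, the SE of the difference is 0.139. Two-sided 5% power is Φ(0.2/0.139 − 1.96), about 30%. It is 23% at correlation 0 and 38% at 0.5. The stated figure is therefore attainable, but the plan gives neither alpha, sidedness nor the correlation.

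**3. Illustration of carry-over.** From section 9.3: AUC 0.70 for b-mode and 0.70 + 0.20 = 0.90 for CESR. Assumed: binormal scores, weight w of 10% or 25% on the first reading, noise correlation r of 0 or 0.3.
- d = √2·Φ⁻¹(AUC), so 0.742 for b-mode and 1.812 for CESR.
- Second score = (1−w)·own + w·first.
- d_eff = [(1−w)·d_own + w·d_first] / √[(1−w)² + w² + 2w(1−w)r], and AUC = Φ(d_eff/√2).
- Example, CESR first, w = 0.25, r = 0: (0.75×0.742 + 0.25×1.812)/√0.625 = 1.277. The b-mode AUC is Φ(0.903) = 0.817, and the difference is 0.083.

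| w | r | CESR first: b-mode AUC (difference) | B-mode first: CESR AUC (difference) | True 0.70/0.70: gain of second-read modality |
|---|---|---|---|---|
| 10% | 0 | 0.746 (0.154) | 0.909 (0.209) | 0.019 |
| 10% | 0.3 | 0.740 (0.160) | 0.901 (0.201) | 0.013 |
| 25% | 0 | 0.817 (0.083) | 0.916 (0.216) | 0.046 |
| 25% | 0.3 | 0.797 (0.103) | 0.898 (0.198) | 0.029 |

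**4. Scale.** The sampling SD of the five-reader mean AUC difference was simulated (20,000 runs, 8 malignant and 7 benign, assumed inter-reader noise correlation 0.3 to 0.7).
- At 0.70/0.90 the SD is 0.09 to 0.13. The CESR-first shift is about 0.3 to 0.5 SD at 10% and 0.8 to 1.1 SD at 25%.
- At 0.70/0.70 the SD is 0.11 to 0.16. The false gain runs from 0.013/0.141 = 0.09 to 0.046/0.125 = 0.37, or about 0.1 to 0.4 SD.

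No matching figures are given for sensitivity and specificity. The plan fixes the cut at +1 and above, and the documents do not show how readers would use that scale.

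**The case against.** - **One form is not one sitting.** Correct. The scores could be entered on different days. The finding is only that nothing in the plan prevents joint or sequential reading. A reader might infer that the readers will see both modalities together; the documents do not say so.
- **The form may be incomplete as extracted.** The items refer to features the reader described, yet no description field appears, and the contents list gives Appendix A about four pages. This stands as a caution. It does not explain why sections 4.2.5 and 9, where reading rules belong, are silent.
- **The preference items need both images.** Yes, by design (objective 2.2.4). They are not a defect in themselves. What matters is when they are taken relative to the malignancy scores.
- **The plan compares scores for each modality, and the F-test is limited to b-mode and CESR images.** That wording names what is compared. It suggests separate scores were intended, but sets no order, masking or lock.
- **This is a pilot with about 30% power, meant to guide a later trial.** True, so no confirmatory decision rests on it. But the planned intervals show random error and would not show this bias.

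**Conclusion.** The point holds as a correctable gap in the reading procedure. Used as written, the form permits carry-over into objectives 2.2.1 to 2.2.3. If b-mode is read first or alongside, it also affects what the primary CESR sensitivity and specificity mean. Neither the bootstrap nor the DBM model removes or reveals it.

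The size is unknown, and the weights above are assumptions. On them, only CESR-first reading has a material effect on the AUC contrast, cutting 0.20 to about 0.08 to 0.16. B-mode-first reading moves it by at most about 0.02. With no true difference, the false gain is about 0.01 to 0.05, well inside sampling error.

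A reader might infer that the design inflates CESR. The documents do not support that: the order is open, the order implied by section 9.4 works against CESR, and the modelled inflation is small. Nor does acquiring b-mode first establish that it is read first.

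**What to change.** Before the first read, which follows accrual:
1. Define Primary and Secondary on the form.
2. Take each malignancy score and confidence on its own dated, single-modality form. Lock it before the other modality of that lesion is opened.
3. Read the modalities in separate blocks. Alternate block order across the five readers and record it; the split is necessarily 3:2. The sponsor should set the interval between blocks in advance.
4. Complete the preference items last, after both scores are locked.

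Minimum acceptable version: fix and record the order, lock the first score before the second modality is opened, and label the second score as read after the first. This protects the first score only.

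If joint reading is intended, describe the CESR results as CESR read with b-mode in objectives 2.1 and 2.2 and in section 9.

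Cost: a second short reading pass, some delay, and readers who stay available through the interval. Malignancy scores remain at 15 × 2 × 5 = 150 per organ. Cases are reopened for the preference items, 15 × 5 = 75 viewings per organ. No extra readers, patients or procedures are needed.
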